5.6 Denominator

Unless otherwise mentioned, denominator of percentage in each table will be the number of population designated in each table.

6 Subject Disposition

6.1 Summary Table of Subject Disposition		
Population	:	All subjects screened
Contents	:	
 • The number of all subjects screened • The number of all subjects dosed with Alpha-1 MP (Safety population) • The number and percentage of all subjects in PK population

6.2 Summary Table of Subjects Who Discontinue from the Study		
Population	:	Safety population
Contents	:	
 • The number and percentage of subjects who complete the study • The number and percentage of subjects who discontinue from the study by reason for discontinuation

Disposition status will be listed for all subjects. A listing will also be provided for screening failure subjects.

7 Protocol Deviations

7.1 Summary Table of Protocol Deviations		
Population	:	Safety population
Contents	:	
The number and percentage of deviations by type and severity will be summarized. Deviations from the protocol will be identified during the study and discussed in the data review meeting. Protocol deviation is defined in “GTI1401 and OLE Protocol Deviation Guidance_24Oct2016_Biling_Clean.pdf”
 
Listing of all deviation.

8 Demographics

8.1 Summary Table of Demographics	
Population	: Safety population
Contents	: For continuous variables, mean, standard deviation, median, and minimum/maximum will be provided. For categorical/qualitative data, frequency counts will be provided (For pregnancy status, the percentage of population is not included). Listing of following contents is provided separately. 
 • Demographics (including alpha₁- Antitrypsin Deficiency history) • Smoking history • Medical history
Analysis variables	: Contents, category and digit to be displayed are showed in the following table.

Contents	Category	Digits to be displayed
Sex	Male Female	
Age [years]		Integer
Race	Asian	
Weight [kg]		1 decimal place
Height [cm]		1 decimal place
Pregnancy status	NA (Males are included in this category) Negative Positive	
Smoking status	Never Former (>100 cigarettes or equivalent of tobacco in subject's lifetime) Current (not eligible for study)	
Total alpha ₁ -PI serum level at time of diagnosis [mg/dL]		1 decimal place
Time since First Diagnosis of alpha ₁ -Antitrypsin Deficiency [years]		1 decimal place
Best FEV ₁ [L] at Baseline		2 decimal place
Best FVC [L] at Baseline		2 decimal place
FEV ₁ Predicted [%]	0=< < 30 30=< < 70 70=< <100	
FEV ₁ Predicted [%]		1 decimal place

15th Percentile of lung Density [g/L]		1 decimal place
Mean lung density [g/L]		1 decimal place

9 Treatments and Medications

9.1 Prior and Concomitant Medications

Definition of prior medication and concomitant medication for GTI 1401

Prior medications are defined as any medication which ended before the first infusion of study drug of GTI 1401.

Concomitant medications are defined as any medication which is started on or after the first infusion of study drug of GTI 1401 or any medication taken prior to the first infusion of study drug of GTI 1401 and continued after the first infusion of study drug of GTI 1401.

Definition concomitant medication for GTI 1401-OLE

Concomitant medications are defined as any medication which is started on or after the first infusion of study drug of GTI 1401-OLE or any medication taken prior to the first infusion of study drug of GTI 1401-OLE and continued after the first infusion of study drug of GTI 1401-OLE.

9.1.1 Summary Table of Prior and Concomitant Medication

Population	:	Safety population
Contents	:	
Summaries of all medications taken during the course of the study will be presented in tabular form and coded using ATC classification codes via the World Health Organization Drug classification Dictionary (WHO-DD). All medications will be summarized and sorted alphabetically by medication class (i.e., ATC level 2) and medication sub-class (i.e., ATC level 4). If the ATC level 4 term is missing, the ATC level 3 term will be used in the medication summary table and data listing.
 
For the summary tables, if a subject has taken a concomitant medication more than once, the subject will be counted only once.
 
All medications will be listed by subject. New medications starting after the first infusion will be indicated if the medication start date relative to the first study drug infusion is greater than 0 in the subject data listing.

9.2 Extent of Exposure

9.2.1 Summary Table of Drug Exposure

Population	:	Safety population
------------	---	-------------------

Contents	: Following contents regarding to exposure information are summarized. Digits to be displayed are showed in Table A
----------	---

- Treatment duration [Week]
- Number of infusions received
- Total volume infused [mL]
- Volume infused per week [mL]
- Infusion duration [Minute]

Treatment duration in weeks is calculated as:
(The Last Dose Date – The First Dose Date + 7) / 7

Volume infused per week is calculated as:
the Total Volume Infused [mL] / the Treatment Duration [Week]

Infusion Duration is calculated as:
the Infusion Stop Time [HH:MM] – the Infusion Start Time [HH:MM] + 1

For Infusion Duration, the summary statistics will be calculated for mean duration of each week.

A list will be provided for Alpha-1 MP dose, volume prepared, and volume infused.

Table A:

Contents	Digits to be displayed
Treatment duration [week]	1 decimal place
Number of infusions received	Integer
Total volume infused [mL]	1 decimal place
Volume infused per week [mL]	1 decimal place
Infusion duration [minute]	Integer

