4.3.1.3 Content and dosage form

Alpha-1 MP is a stable, sterile, lyophilized preparation of human alpha₁-PI, also known as α₁-antitrypsin. Alpha-1 MP is supplied as a white to beige, lyophilized powder contained in a glass vial. Each vial of Alpha-1 MP contains the labeled amount of functionally active alpha₁-PI in milligrams per vial (each vial contains approximately 1,000 mg of functionally active alpha₁-PI). Alpha-1 MP contains no preservatives. Alpha-1 MP is reconstituted using a dissolving solution (20 mL of water for injection) as instructed in the Pharmacy Manual. Alpha-1 MP must be administered by an intravenous route.

Further information on the investigational drug is provided in the investigator's brochure.

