4.3.3 Dose and Dosage Regimen

4.3.3.1 Dose and dosage regimen

Subjects will receive a total of 8 IV infusions of 60 mg/kg Alpha-1 MP administered weekly. The prescribed infusion rate for Alpha-1 MP is not to exceed 0.08 mL/kg/min as determined by the response and comfort of the subject. The recommended dose for this trial takes approximately 15 minutes per IV bag to infuse (based on ~70 kg subject).

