4.2 Study Variables

No efficacy variables will be assessed for the studies. The variables to be assessed for GTI1401 and GTI1401-OLE studies are as follows:

- Adverse events, ADRs, serious AEs (SAEs), and discontinuations due to AEs or SAEs
- Vital signs (heart rate, blood pressure, respiratory rate, and temperature)
- COPD exacerbations
- Pulmonary function tests :
 - Forced Expiratory Volume in 1 second (FEV₁)
 - Forced Vital Capacity (FVC)
- Clinical laboratory parameters:
 - Chemistry
 - Hematology
 - Urinalysis
- Alpha₁-PI trough level
- PK parameters (GTI1401 study only):
 - AUC_{0-7 days}
 - C_{max}
 - t_{max}

- $t_{1/2}$
- CT scan (densitometry)

5 General Statistical Considerations

All analyses will be conducted using SAS Version 9.3 or higher.

Pharmacokinetic evaluations, descriptive statistical analysis of concentrations and PK parameters according to non-compartmental standard methods, as well as graphical representation of concentrations will be performed using the computer program Pharsight Phoenix WinNonlin (Version 6.1 or higher).

Unless otherwise specified, the results from GTI1401 and GTI1401-OLE will be presented separately.

Unless otherwise noted, for continuous variables, descriptive statistics will include the number of non-missing values, mean, standard deviation, median, minimum and maximum. For categorical variables, descriptive statistics will include counts and percentages per category.

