 9.1 Prior and Concomitant Medications
 9.1.3 Listing of Medications

Safety population

Subject Number	Start Date of Study	Concomitant Medications Start Date [1]/ End Date [2]	Route/ Dose [Units]/ Frequency	Who Drug ATC level 2 term/ Who Drug ATC level 4 term/ Preferred Term/ Reported Term	Indication
xx	yyyy-mm-dd	yyyy-mm-dd [88] * yyyy-mm-dd [88]	ORAL	vvvvvvvvvv / xxxxxxxxxx / yyyyyyyyy / zzzzzzzzzzzzzzzz	ADVERSE EVENT (XXXXXXXXXXXXXXXX) / PFT
		yyyy-mm-dd [88] yyyy-mm-dd [88]	INJECTION	vvvvvvvvvv / xxxxxxxxxx / yyyyyyyyy / zzzzzzzzzzzzzzzz	OTHERS (XXXXXXXXXXXXXXXX)
xx	yyyy-mm-dd	yyyy-mm-dd [88] * yyyy-mm-dd [88]	OTHER (SPECIFY)	vvvvvvvvvv / xxxxxxxxxx / yyyyyyyyy / zzzzzzzzzzzzzzzz	ADVERSE EVENT (XXXXXXXXXXXXXXXX) /
...

* New medications starting after the first infusion will be indicated if the medication start date relative to the first study drug infusion is greater than 0

[1] Study start date =< medication start date: medication start date - study start date + 1
 Study start date > medication start date: medication start date - study start date

[2] Study start date =< medication end date: medication end date - Study start date + 1
 Study start date > medication end date: medication end date - Study start date

>Sort order;
 Subject Number, Concomitant Medications Start Date, ATC term, Preferred Term (both alphabetical order)

GTI 1401
 9 Treatments and Medications

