 9.2 Extent of Exposure
 9.2.1 Summary Table of Drug Exposure

Safety population

Parameter	Statistics
Treatment duration [week]	
N	xx
Mean(S.D.)	xx (xx x)
Median	xx x
Min , Max	xx , xx
Number of infusions received	
N	xx
Mean(S.D.)	xx (xx x)
Median	xx x
Min , Max	xx , xx
Total volume infused [mL]	
N	xx
Mean(S.D.)	xx (xx x)
Median	xx x
Min , Max	xx , xx
Volume infused per week [mL]	
N	xx
Mean(S.D.)	xx (xx x)
Median	xx x
Min , Max	xx , xx
Infusion duration [minute]	
N	xx
Mean(S.D.)	xx (xx x)
Median	xx x
Min , Max	xx , xx

GTI 1401

9 Treatments and Medications

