 9.2 Extent of Exposure
 9.2.3 Listing of Exposure Information

Safety population

Subject Number	Visit	Study Drug Infused/ Reason for No Study Drug Infused	Infusion Start Date and Time/ Infusion Stop Date and Time (including saline flush)	Infusion Duration [Minutes]	Total Volume Prepared [mL]/ Total Volume Infused [mL]	Infusion Interrupted / Explanation for Interruption	Reason for less than 100% of IP
xx	Week 1	Y	yyyy-mm-ddThh:mm/ yyyy-mm-ddThh:mm	xx x	xxxx/ xxxx	N	
	Week 2	xxxxxxxxxxxxxx	yyyy-mm-ddThh:mm/ yyyy-mm-ddThh:mm	xx x	xxxxxxxx/ xxxx	xxxxxxxx	
xx	Week 1	Y	yyyy-mm-ddThh:mm/ yyyy-mm-ddThh:mm	xx x	xxxxxxxx/ xxxx		xxxxxxxx
	Week 2	Y					

>Sort order;
 Subject Number, Visit

GTI 1401
 9 Treatments and Medications

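### SAP 9.2.1 adds 1 minute to every infusion duration by computing stop time minus start time plus 1

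*SAP*

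**What the plan says.** SAP 9.2.1 (Summary Table of Drug Exposure) lists infusion duration among five exposure items, gives its unit as minutes, and computes it as the stop time minus "the Infusion Start Time [HH:MM] + 1". It adds that "the summary statistics will be calculated for mean duration of each week". Table A in the same section displays the item as an integer, and the Layout Plan for table 9.2.1 has a row headed "Infusion duration [minute]" with N, mean (SD), median, minimum and maximum.

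The Layout Plan for listing 9.2.3 prints start and stop times beside a duration column. The stop-time heading is "Infusion Stop Date and Time (including saline flush)". The listing states no formula for its duration column.

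No footnote or other section explains or removes the added 1. Section 9.2 is not restricted to the main study, as section 10.1 is, and SAP section 5 says that, unless otherwise specified, "the results from GTI1401 and GTI1401-OLE will be presented separately". The formula therefore also governs the extension's exposure table.

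**The concern.** Adding 1 is correct when units are counted inclusively, as in study-day numbering, where the first day is Day 1. The SAP uses it that way in listing 9.1.3: "medication start date - study start date + 1". A duration in minutes between two clock times is an elapsed interval, and there the extra unit is simply an error.

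What is at stake is small but systematic. Every infusion record is affected: 8 per completing subject in the main study, so 3 × 8 = 24 for the minimum of 3 subjects, and in the extension up to 1 + 51 = 52 per subject through Ext Week 52. The exposure table would state durations that the recorded times do not support.

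**Working it through.** **Inputs**

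- Formula and unit: SAP 9.2.1.
- Dose of 60 mg/kg and rate limit: Protocol 4.3.3.1 ("The prescribed infusion rate for Alpha-1 MP is not to exceed 0.08 mL/kg/min").
- Vial content of approximately 1,000 mg and its volume: Protocol 4.3.1.3 ("Alpha-1 MP is reconstituted using a dissolving solution (20 mL of water for injection)").
- Saline flush of at least 25 mL: Protocol 4.4.3.
- PK sampling times: time table in SAP 10.1.

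**1. Reproduce the protocol's infusion time.** Protocol 4.3.3.1 gives about 15 minutes for a subject of about 70 kg.

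- Concentration: 1,000 / 20 = 50 mg/mL.
- Volume: 60 / 50 = 1.2 mL/kg.
- Time at the rate limit: 1.2 / 0.08 = 15.0 minutes. For 70 kg this is 84 mL at 5.6 mL/min.

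The figure reproduces. The SAP 10.1 time table agrees with it: the pre-infusion sample is at nominal 0 h and the sample immediately after the infusion at 0.25 h, which is 15 minutes with no added minute.

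**2. Size of the excess.** With D = stop − start in minutes, the SAP rule gives D + 1, so the relative excess is 1/D.

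| D (min) | SAP rule | Excess | Source of D |
|---|---|---|---|
| 15 | 16 | 1/15 = 6.7% | nominal 50 mg/mL at the rate limit, no flush |
| 18 | 19 | 1/18 = 5.6% | 0.30 h × 60, the SAP 10.1 example for the post-flush sample |
| 20 | 21 | 1/20 = 5.0% | illustrative |
| 30 | 31 | 1/30 = 3.3% | illustrative |

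**3. Effect on the table.** A constant shift moves every measure of location by the same amount and leaves the spread alone. For example durations of 15, 18, 20, 22, 25 and 30 minutes:

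- mean 21.67 → 22.67
- median 21 → 22
- minimum 15 → 16
- maximum 30 → 31
- SD 5.32 → 5.32

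Averaging durations by week first does not change this, because the average of values that are each 1 too high is also 1 too high.

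**4. Does recording to the minute justify the added 1?** Suppose both clock times are truncated to the minute, losing fractions u (start) and v (stop). Then recorded stop − start = true duration + u − v. If u and v have the same average, the mean error is 0, and adding 1 makes it +1 minute. A simulation of infusions lasting 15 to 40 minutes with both times truncated agrees: the mean error was 0.00 for stop − start and +1.00 with the added 1. This holds only if both times are rounded in the same way.

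**The case against.** The strongest objection is materiality. This is one of five descriptive exposure items in a study with no efficacy variables and a target of at least 3 subjects. The rule is prespecified, the shift is constant, and listing 9.2.3 prints the raw times, so any reader can recover stop minus start. All of that stands. It limits the severity but does not make the formula right.

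It can also be said that the SAP openly defines duration by inclusive counting of minutes. The SAP gives no such reason, and its own PK time table treats the infusion as an elapsed interval.

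On rounding, if sites rounded start times up and stop times down, stop minus start would average 1 minute too short and the added 1 would offset that. The documents do not say how times are rounded, and nothing in them points to this pattern.

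A reader might make two inferences that go too far:

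- **That +6.7% is a ceiling.** It depends on exactly 50 mg/mL, while vial content is only approximate. An assumed 900 to 1,100 mg per vial gives 16.7 to 13.6 minutes at the rate limit, and so 6.0% to 7.3%. It also leaves out the flush, which the recorded stop time includes. If 25 mL ran at the same maximum rate in a 70 kg subject (an assumption), D would be 15 + 25/5.6 = 19.5 minutes and the excess 5.1%.
- **That listing 9.2.3 must contradict itself.** Its printed times will fail to subtract to its printed duration only if it uses the 9.2.1 formula. That is likely, but the documents do not state it.

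**Conclusion.** The formula is wrong as written, and the point is minor. Every derived infusion duration exceeds the recorded clock difference by exactly 1 minute. This follows from the formula alone. The percentages are illustrations that depend on the actual durations, and the statement that plain subtraction is unbiased assumes that both times are rounded alike.

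A reader might infer that a wrong duration carries into the pharmacokinetic or safety results. The documents do not support that. PK parameters use actual sampling times, with elapsed time measured from the start of the infusion. Treatment compliance uses volumes and infusion compliance uses counts. No adverse-event analysis uses infusion duration.

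**What to change.** In SAP 9.2.1, delete the added 1 so that infusion duration in minutes is the stop time minus the start time. State that listing 9.2.3 uses the same formula, so that its printed times and durations agree. The change applies to the main study and the extension alike. It costs one formula edit and needs no new data and no new output.

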9.2.2 Summary Table of Infusion Interruptions

Population	:	Safety population
Contents	:	The number and percentage of infusion with interruptions will be summarized by analysis visit. Reasons for interruptions will be displayed in the listings.

9.3 Treatment Compliance

Treatment compliance will be calculated as:

$$\frac{\text{Total Volume Infused}}{\text{Total Volume Prepared}} \times 100\%$$

The total volume prepared is collected on the eCRF and is calculated based on the subject's weight at baseline.

The total volume prepared and dispensed by pharmacist is the intended dose volume a subject should be given based on the body weight.

Infusion compliance will be calculated as:

$$\frac{\text{The Number of Actual Infusions}}{\text{The Number of Infusions Expected}} \times 100\%$$

For subjects who drop out from the study early, the number of infusions expected will depend on the number of weeks the subjects are in the study.

9.3.1 Summary Table of Treatment Compliance		
Population	:	Safety population
Contents	:	Following contents will be displayed. 
 • Summary of treatment compliance [%] • The number of subjects with treatment compliance $\geq 80\%$ • Summary of infusion compliance [%] A listing of treatment compliance will be provided.

10 Exploratory Analysis

10.1 PK Analysis (GTI1401 only)

Alpha₁-Proteinase Inhibitor (alpha₁-PI) concentrations in serum will be measured by validated content assay. The concentration data will be presented and summarized. Time points recorded on CRF will be used as analysis time points.

Time Table for Week 8 and Week 9

Visit	Actual elapsed time (real-time)	Nominal time point (numeric version) (hours)	Scheduled time point
-------	---------------------------------	--	----------------------

Visit	Actual elapsed time (real-time)	Nominal time point (numeric version) (hours)	Scheduled time point
Week 8	0	0	Immediately before the intravenous infusion
Week 8	0.30	0.25	Immediately after the intravenous infusion (after flushing the infusion line with physiological saline) (at 0 hours)
Week 8	0.55	0.5	15 minutes after completion of the intravenous infusion
Week 8	2.35	2.25	2 hours after completion of the intravenous infusion
Week 8	4.67	4.25	4 hours after completion of the intravenous infusion
Week 8	8.67	8.25	8 hours after completion of the intravenous infusion
Week 8	26.02	24.25	24 ± 4 hours (1 day after completion of the intravenous infusion)
Week 8	49.17	48.25	48 ± 4 hours (2 days after completion of the intravenous infusion)
Week 8	120.58	120.25	120 hours ± 1 day (5 days after completion of the intravenous infusion)
Week 9	169.50	168.25	168 hours ± 1 day (7 days after completion of the intravenous infusion) (Week 9)

10.1.1 Summary Table of Alpha₁-PI Concentrations

Population	:	PK population
Contents	:	Alpha ₁ -PI concentrations will be summarized. The summaries will include n, mean (SD), coefficient of variation (%CV) (=SD/Arithmetic mean), median, minimum, maximum as well as geometric mean.
Digit	:	2 decimal places will be displayed for summary table of alpha ₁ -PI Concentrations.
Analysis	:	
 Immediately before the intravenous infusion

visit	
 • Immediately after infusion completion (after sodium chloride [NaCl] flush) (0 hour) • 15 minutes after infusion completion • 2 hours after infusion completion • 4 hours after infusion completion • 8 hours after infusion completion • 24±4 hours (1 day after infusion completion) • 48±4 hours (2 days after infusion completion) • 120 hours ± 1 day (5 days after infusion completion) • 168 hours ± 1 day (7 days after infusion completion) (Week 9 Visit) 
Serum concentrations of alpha₁-PI determined by content assay will be presented in a listing by subject, study week, and scheduled or nominal time point.
 
This data listing will provide details of all planned plasma collection time points (scheduled and nominal times as specified in Section 12.1), actual collection date and clock times and elapsed times from the start of the study drug infusion, as well as alpha₁-PI concentrations. Samples excluded from PK analysis will be flagged.
 
The date/clock time for the start and completion of study drug infusion, the actual volume infused, and the actual dose infused (mg/kg) at Week 8 (PK assessment visit) will be presented in a separate listing.

-------	--

10.1.2 Summary Table of Trough (pre-infusion) Levels (C_{min}) and mean C_{min}	
Population	: PK population
Contents	
This table include following contents.
 
 • Summary of trough (pre-infusion) levels (C_{min}) and mean C_{min} at steady state by week number (for C_{min}). 
Mean C_{min} calculated by the trough levels from weeks 7, 8, and 9 (exclude Week 1).
 
 • Number and Proportion with mean C_{min} of alpha₁-PI Concentration \geq 50 mg/dL (=11.3 μM nearly equal to 11μM which is defined in ATS/ERS statement in 2003). A conversion factor of 0.226 based on the protein only molecular weight of 44.3 KDa for alpha₁-PI is used for converting mg/dL to μM (i.e., 1 mg/dL alpha₁-PI = 0.226 μM). 
No data imputations will be involved in the above concentration data listings, summaries, or figures.
 
Trough (pre-infusion) levels (C_{min}) and mean C_{min} at steady state will

		be listed
Digit	:	2 decimal places will be displayed for summary table of C_{\min} .
Analysis visit (only C_{\min})	:	Week 1, Week 7, Week 8 and Week 9, *mean C_{\min} = Average of C_{\min} of each patient measured at Week 7, Week 8 and Week 9 (exclude Week 1)

10.1.3 Figures of Concentration Versus Time Curves of Individual Subjects

Population	:	PK population
Contents	:	For concentration data, serum alpha ₁ -PI concentration versus time curves following 8 weeks of treatments in individual subjects will be presented in one figure with the actual elapsed time from the start of the study drug infusion plotted on the x-axis.

10.1.4 Figures of Concentration Versus Time Curves of All Subjects

Population	:	PK population
Contents	:	For all subjects combined, mean or median plasma alpha ₁ -PI concentration versus time curves following 8 weeks of treatments will be presented in one figure with the nominal time plotted on the x-axis.

All serum alpha₁-PI concentration vs. time curves will be plotted on both linear and semi-log scales.

A spaghetti plot (on the linear scale only) will be presented for all subjects following 8 weeks of treatment for concentration values vs nominal time.

Calculation of PK Parameters

The pharmacokinetic profiles of alpha₁-PI following weekly administration of Alpha-1 MP will be characterized by pharmacokinetic parameters, including area under the curve (AUC) at steady state following 8 weeks of weekly infusions (AUC_{0-7days}), maximum concentration (C_{max}), time to first observed maximum concentration (t_{max}), and half-life (t_{1/2}), based on alpha₁-PI concentrations in serum measured using content assay.

All PK parameters will be calculated using non-compartmental methods with WinNonlin software (Pharsight Corporation, Cary NC).

The pharmacokinetic parameters of interest are determined as follows:

- | | |
|------------------------|--|
| AUC _{0-7days} | area under the concentration vs. time curve at steady state over the weekly dosing interval (time 0 to 7 days), calculated by a combination of linear and logarithmic trapezoidal methods and expressed in the unit of concentration x time (mg·hr/dL). The linear trapezoidal method will be used for all incremental trapezoids arising from increasing concentrations and the logarithmic trapezoidal method will be used for those arising from decreasing concentrations. |
| C _{max} | the first observed peak serum alpha ₁ -PI concentration following drug infusion obtained directly from the experimental data without interpolation, expressed in concentration units (mg/dL). |
| t _{max} | the observed time to reach peak serum alpha ₁ -PI concentration obtained directly from the experimental data without interpolation, expressed in time units (hour). If there are more than one maximum observed concentration, the t _{max} is the time to the first observed peak concentration. |
| t _{1/2} | the terminal half-life, calculated as (ln2)/K _{el} , expressed in time units (hour). The apparent terminal first-order elimination rate constant, determined by linear regression analysis of the natural log-linear segment of the plasma concentration-time curve, expressed in time ⁻¹ units (1/hour). At least 3 time points over 7 days following the treatment at week 8 will be included in the determination of K _{el} (Points prior to C _{max} or prior to the end of infusion are not used). |
| C _{min} | the observed serum concentrations prior to the start of infusions obtained at Weeks 7, 8 and at 7 days (168 hours) post infusion at Week 8, expressed in concentration units (mg/dL). |

Mean C_{\min} the average trough concentration at steady state, calculated as the mean value using the three C_{\min} measurements obtained at Weeks 7, 8 and at 7 days (168 hours) post infusion at Week 9.

Analysis of PK Parameters

For PK parameters descriptive statistics and geometric mean (except t_{\max}) will be calculated.

